### 3.6 Primary Safety Endpoints

The primary safety endpoint of this study will be the number of days between unintentional mucosal and/or ocular exposure during the study period.

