## **5.2 Treatment Regimen**

All study participants will apply Valchlor 0.016% gel to involved areas at night, beginning with three times a week, (Mondays, Wednesdays and Fridays) and increasing to daily application after one month, if well tolerated, for a total of 6 months. Patients will be instructed to first part the hair away from involved area as needed, limit application to areas with alopecia and erythema, apply 30 minutes after showering or washing, and allow treated areas to dry for 5 to 10 minutes before covering with clothing or going to bed. Participants will be instructed to wash their hands with soap and water after applying Valchlor. Caregivers who assist in application will be instructed to wear disposable nitrile gloves when applying Valchlor and dispose with the household trash. Patients will be instructed to store Valchlor in the refrigerator away from foods at 36-46 degrees F and apply within 30 minutes after removing from refrigeration.

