### 6.3 Visit 4 (Week 24± 5 days)

- a) LPPAI score final
- b) PGA score final
- c) DLQI score final
- d) Review changes to medical history and current medications
- e) Screen/review adverse events
- f) Repeat photographs
- g) Assessments of hair density using phototrichograms
- h) Reconcile and collection of unused study drug
- i) Urine Pregnancy Test (female patients of childbearing potential); confirm form of contraception

Study Activity	Schedule of Events			
	Day 1 SCREENING BASELINE	Week 4 PHONE FOLLOW- UP	Week 12 FOLLOWUP	Week 24 FOLLOWUP
Visit Number	1	2	3	4
Allowable visit window in days		+/- 5	+/- 5	+/- 5
Review Eligibility	X			
Informed Consent	X			
Medical History	X			
Dispense/Reconcile Medications	X	X	X	X
Review Changes to Med History and Medications			X	X
LPPAI	X		X	X
PGA	X			X
DLQI	X			X
B-HCG (females)	X		X	X
Photographs/Hair Count	X		X	X
Review Valchlor Application Instructions	X		X	X
Screening for Adverse Events		X	X	X

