## **7 Statistical Plan**

### **7.1 Sample Size Determination**

Due to the pilot nature of the study, no formal statistical power or sample size calculations are necessary. The sample size of 20 patients will be sufficient for this pilot study to obtain a preliminary estimate of treatment efficacy and to generate data that will be useful in the design of a larger study.

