#### Adverse Event

An AE is defined as any untoward medical occurrence in a patient administered a pharmaceutical product and which does not necessarily have a causal relationship with the treatment. An AE can therefore be any unfavorable and unintended sign (including an abnormal lab finding), symptom or disease temporally associated with the use of a medicinal product, whether or not related to the medicinal product.

Each AE must be assessed by the investigator as to whether or not there is a reasonable possibility of causal relationship to Valchlor, and documented as either related or unrelated. The determination of the likelihood that Valchlor caused the AE must be provided by an investigator who is a qualified physician. .

Initial screening for AE will include non-directed questioning of the patient at each follow-up visit during the study period along with the directed questioning and examination regarding:

- Signs and symptoms of idiosyncratic allergic contact dermatitis

Patients will be instructed to stop using Valchlor and to contact the study coordinator if swelling and blistering occurs as this may represent early signs of allergic contact dermatitis. The primary investigator will then evaluate the patient and if the signs and symptoms are

compatible with allergic contact dermatitis, the patient will be offered treatment using a medium-potency topical corticosteroid to involved areas in the AM, with resumption of Valchlor application in the PM. Patients with persistent allergic contact dermatitis reactions unable to be managed as outlined above will exit the study.

- Unintentional mucosal and/ocular exposure

Patients will be warned not to apply Valchlor near eyes, mouth, or nose as it can cause pain, redness, swelling, burning, sensitivity to light, blurred vision, and blindness or permanent eye injury. If accidental Valchlor exposure to nose, mouth or eyes occurs, patients will be instructed to rinse affected areas with large amounts of water for 15 minutes and to contact the study coordinator. The primary investigator will then contact the patient to review application site instructions and schedule a follow-up evaluation if the patient reports persistent symptoms or erythema.

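### The primary safety endpoint counts days between exposures with no application denominator, so it mixes risk per application with an application frequency that changes during the study

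*Combined protocol and SAP*

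**What the plan says.** Section 3.6 names one primary safety endpoint: "the number of days between unintentional mucosal and/or ocular exposure during the study period". The unit is days, most naturally calendar days. The section does not say whether gaps are taken within a participant or across the cohort.

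Sections 3.1 and 5.2 set the schedule. Participants begin with three evenings a week, "increasing to daily application after one month, if well tolerated, for a total of 6 months". Frequency therefore changes within a participant by design, and between participants according to tolerability. Section 8.1 (Adverse Event) adds another source of variation: "Patients will be instructed to stop using Valchlor and to contact the study coordinator if swelling and blistering occurs". Application may resume after evaluation.

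Section 7.2 gives generic descriptive summaries. It contains nothing specific to this endpoint: no count of applications, no allowance for frequency and no split by period. Section 7.1 says that the 20 participants should yield data useful for designing a larger study.

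**The concern.** Accidental contact with the eyes or mucosa is, on any ordinary reading, something that happens when the gel is applied or shortly afterwards. The number of opportunities per day is then part of what determines the gap between exposures. An endpoint in days absorbs that number without reporting it.

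Two cohorts with the same risk at each application would give different results if one stepped up and the other did not. The cohort that tolerated the step-up poorly would tend to show longer gaps and so look safer. A planner of a larger study could not separate the risk of an application from the unreported mix of frequencies behind the figure.

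**Working it through.** The documents give no exposure rate, expected gap or precision for this endpoint, so there is no figure of theirs to reproduce.

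**Inputs**
- Three applications per 7 days, then seven per 7 days (5.2).
- Follow-up of 24 weeks, or 168 days (6.3), and 20 participants (7.1).
- Assumed: the month before step-up is 28 days, and risk *p* per application is constant, from 0.1% to 5%.

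**Underlying rate.** Expected exposures per day are 3*p*/7 at three a week and *p* at daily use. The ratio is 7/3 = 2.33 for any *p*. The corresponding uncensored mean gaps are 7/(3*p*) and 1/*p* days.

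**Scheduled applications over 24 weeks**
- Stepped up at day 28: 4 × 3 + 20 × 7 = 152.
- Never stepped up: 24 × 3 = 72.
- Ratio: 152/72 = 2.11. At *p* = 1%, expected exposures per participant are 1.52 and 0.72.
- Taking the month as 30 days gives about 151 instead of 152.

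**Gaps observable inside the study.** A gap needs two exposures within 168 days, so long gaps are cut off. With *n* applications, P(at least two) = 1 − (1 − *p*)^*n* − *np*(1 − *p*)^(*n* − 1). The mean gap was simulated with 200,000 participants per schedule and value of *p*, averaging the gaps within each participant who had at least two exposures.

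| Assumed *p* | Mean gap, never stepped up (days) | Mean gap, stepped up at day 28 (days) | Ratio | Expected participants of 20 with any gap, stepped up |
|---|---|---|---|---|
| 0.1% | 55.2 | 51.8 | 1.07 | 0.2 |
| 0.5% | 55.0 | 49.1 | 1.12 | 3.5 |
| 1% | 53.0 | 45.4 | 1.17 | 9.0 |
| 2% | 49.5 | 37.6 | 1.32 | 16.2 |
| 5% | 37.8 | 20.5 | 1.84 | 19.9 |

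The observed gap thus moves with frequency, but by less than the underlying rate, because the 24-week window compresses it.

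**What an application denominator shows.** With zero exposures, the exact two-sided 95% Poisson upper limit is 3.689 events. If all 20 step up on time there are 20 × 152 = 3,040 applications, and the limit is 3.689/3,040 = 0.12 per 100. If none step up there are 20 × 72 = 1,440, and the limit is 3.689/1,440 = 0.26 per 100. The days-between endpoint has no value in either case.

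**The case against.** A reader might infer that the endpoint itself shifts 2.3-fold by construction, or that gaps will visibly shorten after month 1 and look like worsening safety. The documents do not support either reading.
- The 2.33 is a ratio of uncensored expectations. At *p* = 1% the mean gap at three a week would be 7/(3 × 0.01) = 233 days, longer than the whole study.
- A gap lying wholly in the first 28 days needs two exposures in 12 applications. The probability is 0.00007 at *p* = 0.1% and 0.118 at 5%, or about 0.001 to 2.4 of 20 participants.
- The plan has one arm, no interim analysis, and no comparison of early with late periods or of those who did and did not step up. With timely step-up, 140 of 168 days (83%) are at daily use.

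A reader might also note that scheduled adverse-event contacts at Weeks 4, 12 and 24 follow 12, 56 and 84 applications. That does not bear on the unit: participants are told to call when an exposure occurs (8.1), and missed recall would affect a per-application count equally.

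It can fairly be said that exposure per unit time under the regimen as used is a legitimate safety quantity, and that someone who applies less really does have fewer exposures. This stands. But 3.6 asks for gaps, which are not a rate over all time at risk, and the plan does not report the frequency needed to interpret them. Constant *p* is also an assumption, since application instructions are reviewed at visits and again after an exposure.

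Finally, the gap is undefined for anyone with no exposure or only one. That is arguably the larger defect in the same sentence, and the same replacement cures it.

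**Conclusion.** The concern holds in a limited form. The primary safety endpoint has no application denominator although frequency is planned to change, depends on tolerability and may be interrupted. At constant risk per application, the underlying daily exposure rate varies up to 7/3-fold and scheduled applications from 72 to 152. The effect on gaps observable in 168 days is about 1.1- to 1.8-fold between those extreme schedules, for assumed risks of 0.1% to 5%.

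These sizes rest on exposures arising from applications, a constant risk, a 28-day month and gaps taken within participants. The documents state none of these outright except the approximate month. The direction, with less frequent application tending to look safer, does not depend on the exact value of *p*. This is an interpretive fault in an exploratory pilot that should be corrected. It does not show that the safety result will be wrong by any particular factor.

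**What to change.** In 3.6, with matching text in 7.2, replace the days-between measure with:

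1. the total number of unintentional mucosal or ocular exposures;
2. the number and percentage of participants with at least one, with an exact binomial 95% confidence interval;
3. the rate per 100 scheduled applications, with an exact Poisson 95% confidence interval and a note that it ignores clustering of repeat exposures within participants.

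Count applications from the 5.2 schedule, using each participant's step-up date and any known stop and resume dates. Show the split between three-times-weekly and daily use descriptively only. The first period would hold about 20 × 12 = 240 applications, and two events there would give an exact interval of roughly 0.1 to 3.0 per 100. Phase is also confounded with the participant's experience of applying the gel.

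Exposure dates are already collected as adverse-event dates (8.3.1), and the tube weights in 5.5 offer a rough check on use. The cost is wording and a case report form field for step-up and interruption dates, with no added visit or procedure. The small downside is that scheduled applications only approximate actual ones.

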### 3.7 Identification of Source Data

The following source data will be directly recorded on the Case Report Form (CRF):

- Baseline and interval changes to medical history
- LLPAI score
- DQLI score
- PGA score
- Screening and documentation of Adverse Events
- Phototrichograms for hair count using Fotofinder video-epiluminescence microscopy in combination with the Trichoscan digital image analysis

The following source data will not be directly recorded in the CRF, but will be captured in supportive documentation to include study source documents and the EMR:

- Laboratory results and clinical interpretation of the values
- Standardized clinical photography

## **4 Subject Selection Enrollment and Withdrawal**

### **4.1 Inclusion Criteria**

Informed subject consent will be obtained from those patients meeting the following inclusion criteria:

- Male and female patients 18 years or older.
- Biopsy proven diagnosis of Lichen Planopilaris
- Biopsy proven diagnosis of Frontal Fibrosing Alopecia (a clinical variant of LPP restricted to frontal scalp)
- Good general health as confirmed by medical history
- Patients who are willing and capable of cooperating to the extent and degree required by the protocol; and
- Patients who read and sign an approved informed consent for this study

### **4.2 Exclusion Criteria**

Patients are to be excluded based on the following criteria:

- Vulnerable study population
- Pregnant or nursing women
- Women planning a pregnancy within the study period
- Active smokers
- Known history of adverse reaction to mechlorethamine
- Use of systemic immunosuppressive
- Presence of ulcerated scalp lesions

### **4.3 Subject Recruitment, Enrollment and Screening**

Subjects will be recruited from the Department of Dermatology at the Mayo Clinic in Florida outpatient clinical practice. All referring dermatologic physicians to Mayo Clinic Florida in the Southeastern United States will also be mailed a notice advising of the availability of this study. Patients may be directly referred for participation by these providers with all screening and follow-up exams performed at Mayo Clinic in Florida. Patients will be provided with a Research Participant Consent and Privacy Authorization Form describing the study formulation, protocol, inclusion and exclusion criteria, as well as risks and benefits of participation.

## 4.4 Early Withdrawal of Subjects

### 4.4.1 When and How to Withdraw Subjects

Patients are free to withdraw at any time and for whatever reason. No data will be collected for withdrawn subjects and withdrawn subjects may be replaced within the accrual period. There will be no follow-up for withdrawn subjects. Pre-specified reasons for discontinuing include, but are not limited to, the following:

- Patient Request: Patient decided that he/she did not want to continue (for any reason)
- Adverse Event: Patient experienced a related or unrelated event that would interfere with the study objectives/evaluation
- Lost to Follow-up: Patient did not come in for a visit and could not be reached by phone
- Treatment Failure: If in the Principal Investigator and/or Investigators' judgment, the patient's condition required another form of treatment
- Mechlorethamine sensitization: Patient develops contact dermatitis to Valchlor that cannot be managed with low potency topical corticosteroids
- Inclusion/Exclusion Discrepancy/Violation: Patient should not have been enrolled
- Noncompliance: Patient is not complying with the protocol requirements (i.e. visit schedule, dosing, regimen, etc.); a patient is to be withdrawn if he/she misses two consecutive visits
- Other: Any other reason

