### 3.4 Primary Study Endpoints

The primary outcome measure of efficacy will be the percent reduction of baseline Lichen Planopilaris Activity Index (LLPAI) score after 6 months of treatment defined as follows.

- Complete response: LLPAI reduction greater than 85% from baseline score.
- Partial response: LLPAI reduction of between 25-85% from baseline score.
- Non-response: LLPAI reduction of less than 25% from baseline score.

The Lichen Planopilaris Activity Index (LPPAI) is a standardized validated quantitative measure of disease activity [12]. LPPAI score (0-10) is calculated as follows: (pruritus + pain + burning)/3 + (scalp erythema + perifollicular erythema + perifollicular scale)/3 + 2.5 (pull test) + 1.5 (spreading/2). Symptoms and signs are graded on a 4-point scale with 0 = absent, 1 = mild, 2 = moderate, and 3 =severe. Clinical progression and a positive hair pull test are graded 1=yes; 0=no.

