### **7.2 Statistical Methods**

#### **Descriptive Statistics**

Continuous variables will be summarized using the sample mean, median, standard deviation, interquartile range, and range. Categorical variables will be summarized using number and percentage of patients

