#### **Handling of Missing Data**

This is a prospective study and therefore we do not anticipate any missing data. In the event of any unexpected missing data, no attempt to impute this missing data will be made; missing data will simply be treated as missing in the statistical analysis.

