### **7.3 Subject Population(s) for Analysis**

Each participant who received the study drug will be included in the primary analysis regardless of study withdrawal for any reason. In the event of any study withdrawals, in secondary analysis we will examine the sensitivity of our results to the exclusion of patients who withdrew.

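### Treated participants who withdraw before Week 24 belong to the primary analysis but have no response class, and the denominator of the response percentages is not stated

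*Combined protocol and SAP*

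**What the plan says.** - **Who is analysed.** Section 7.3: "Each participant who received the study drug will be included in the primary analysis regardless of study withdrawal for any reason". The one planned sensitivity analysis is in the same section: "in secondary analysis we will examine the sensitivity of our results to the exclusion of patients who withdrew".
- **What is analysed.** Section 3.4 defines the primary outcome as "percent reduction of baseline Lichen Planopilaris Activity Index (LLPAI) score after 6 months of treatment" and divides it into three classes. The lowest, non-response, is "LLPAI reduction of less than 25% from baseline score". There is no class for a participant without a 6-month score.
- **What is collected after withdrawal.** Section 4.4.1: "No data will be collected for withdrawn subjects and withdrawn subjects may be replaced within the accrual period". Section 4.4.2 adds that the participant will not be contacted again.
- **What happens to missing values.** Section 7.2, Handling of Missing Data, expects none. If there are any, "no attempt to impute this missing data will be made" and "missing data will simply be treated as missing in the statistical analysis".
- **How classes are reported.** Section 7.2, Descriptive Statistics: "Categorical variables will be summarized using number and percentage of patients". No denominator is named.

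Section 9.3 asks for missing CRF entries to be explained but gives no analysis rule. Section 9.1 keeps data collected before a participant revokes authorization; section 4.4.1 does not say the same for other withdrawals.

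**The concern.** Section 7.3 settles who belongs to the primary analysis but not how a participant without a Week 24 LPPAI counts in it. If the missing-data rule is applied by leaving that person out of the percentage, it undoes the all-treated population that section 7.3 sets up.

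The response percentages matter here. Section 7.2 (Primary Hypothesis) makes the response classes the basis for comparison with published hydroxychloroquine and mycophenolate mofetil results, and section 7.1 wants a preliminary efficacy estimate for designing a larger study. With the denominator unstated, the same data support different percentages, and the choice could be made after the results are known.

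The likely direction is upward. Of the eight withdrawal reasons in section 4.4.1, treatment failure is tied directly to poor response, and sensitization that cannot be managed means the drug could not be continued. Replacement can also restore 20 completers and make the loss less visible.

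**Working it through.** **Step 1. Follow one participant through the text.** A participant receives study drug and withdraws before Week 24.

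1. Section 7.3: in the primary analysis.
2. Sections 4.4.1 and 4.4.2: no further data and no contact, so no Week 24 LPPAI.
3. Section 3.4: no 6-month reduction, so no response class. A Week 12 score may exist, but no section carries it forward.
4. Section 7.2: no imputation, so the class stays missing.
5. Section 7.2, Descriptive Statistics: a percentage is reported, over an unstated denominator.

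If missing means left out, the primary percentage uses only those with a Week 24 score. The sensitivity analysis excluding withdrawals then gives the same figure, except where someone recorded as withdrawn nevertheless has a Week 24 score.

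**Step 2. Size, on assumed rates.** The plan has no figure to reproduce: it states no power, dropout rate or response rate. The only input from the documents is 20 participants (section 7.1). Let *w* be the number withdrawn without a Week 24 score and *r* the responders (complete or partial) among completers.

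- Completers only: r/(20 − w)
- All treated, missing not counted as response: r/20
- Best case, all withdrawn counted as responders: (r + w)/20

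Holding the completer rate at 50%:

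| w | Completers only | All treated | Best case |
|---|---|---|---|
| 2 | 9/18 = 50% | 9/20 = 45% | 11/20 = 55% |
| 4 | 8/16 = 50% | 8/20 = 40% | 12/20 = 60% |
| 6 | 7/14 = 50% | 7/20 = 35% | 13/20 = 65% |

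For w = 4 the exact (Clopper-Pearson) 95% intervals are 25–75%, 19–64% and 36–81%. They overlap heavily; what moves is the point estimate.

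Take those 16 completers as 3 complete, 5 partial and 8 non-responses. Complete response alone is then 3/16 = 19% (4–46%), 3/20 = 15% (3–38%) and best case 7/20 = 35% (15–59%).

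**Step 3. Replacement.** Suppose 4 withdraw and are replaced, giving 24 treated and 20 completers with 10 responders. The rate is 10/20 = 50% (27–73%) on completers and 10/24 = 42% (22–63%) on all treated, with best case 14/24 = 58%.

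**Step 4. Direction.** The completers-only rate is too high when fewer than w·r/(20 − w) of the withdrawn would have responded, and too low when more would have. For w = 4 and r = 8 the break-even is 4 × 8/16 = 2.

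**Step 5. Effect per informative withdrawal.** Suppose *k* of the withdrawn are true non-responders and the rest would respond at the completer rate *p*. The all-treated rate is p(20 − k)/20, so the overstatement is p − p(20 − k)/20 = pk/20.

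| p | k = 1 | k = 4 |
|---|---|---|
| 30% | 1.5 points | 6 points |
| 50% | 2.5 points | 10 points |
| 70% | 3.5 points | 14 points |

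With k = 0 there is no overstatement.

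**The case against.** The strongest reply is that the sections, read together, already imply an all-treated denominator. Section 7.3 includes everyone treated, section 7.2 says missing values are treated as missing rather than excluded, and a sensitivity analysis that removes withdrawals makes sense only if the primary analysis still counts them. On that reading missing would be shown as a separate line, both denominators would be reported, and nothing would be left to choose afterwards. This reading is open, but no section states it, and the missing-data sentence supports the opposite reading equally well.

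Several narrower points stand:

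- The problem concerns the response percentages. For the continuous percent reduction, an observed-data summary is acceptable if labelled as such.
- All rates above are assumptions. The 50% against 40% contrast treats all four withdrawals as non-responders, which is a bound. The shift per informative withdrawal is small beside an interval of 19–64%, and the plan has no test or go/no-go threshold that depends on it.
- Most of the listed withdrawal reasons may be unrelated to response.
- The documents do not say how the published comparators handled dropouts, so it is unknown which convention would make that comparison fairer.

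These points limit the weight of the finding but do not close the gap. In a descriptive pilot the point estimate is the result. Being a pilot excuses the absence of a power calculation; it does not excuse an undefined primary percentage.

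**Conclusion.** The concern holds and should be fixed before analysis. That a treated participant without a Week 24 LPPAI has no response class, and that no denominator is given, follows from the text with high confidence. That dropping such participants overstates response is likely rather than certain; it rests on some withdrawals being for treatment failure or sensitization. The size depends on the number of withdrawals, which the documents do not give. Under the assumed 2, 4 or 6 withdrawals of 20 and a completer rate of 50%, the completers-only figure exceeds the all-treated figure by 5, 10 or 15 points. With no withdrawals or other missing Week 24 scores there is no effect.

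**What to change.** 1. **Denominator and class (sections 7.2 and 7.3).** State that the percentages with complete response, and with complete or partial response, use all participants who received study drug, including any later replaced, and that a missing Week 24 LPPAI counts as non-response. Amend the no-imputation sentence to allow this exception. Alternatively, show missing as its own category over the same denominator and leave that sentence alone. The complete and partial percentages are identical either way. Only the non-response line differs: in the example, 12/20 = 60%, or 8/20 = 40% plus 4/20 = 20% missing.
2. **Sensitivity analyses.** Report completers-only, and a best case with missing counted as complete response. Summarize the continuous percent reduction on observed data, labelled so, with the number missing and the reasons.
3. **Data before withdrawal (section 4.4.1).** State that data already collected, including Week 12 LPPAI, are kept.
4. **Separate point, with no bearing on the denominator.** Sections 4.4.1 and 4.4.2 end follow-up and contact at withdrawal, while section 8.1 (Post-study Adverse Event) and section 8.2 require continued follow-up of adverse events. These passages must be reconciled.

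The denominator and sensitivity changes need wording only, with no new visit or assessment. The downside of counting missing as non-response is a lower, conservative rate that also counts administrative losses and eligibility errors as non-response; the completers-only analysis shows how much that matters.

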### 4.4.2 Data Collection and Follow-up for Withdrawn Subjects

If a Participant withdraws from the study, no additional attempts will be made to contact the Participant.

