### 6.2 Visit 2 (Week 4 Phone Follow-up)

- a) Phone follow-up visit to assess any adverse reactions (if any)
- b) Dispense 2 tubes of study drug

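### The attendance-based withdrawal rules in 4.4.1 do not fit the three post-baseline visits and can stop the Week 24 LPPAI from being sought

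*Combined protocol and SAP*

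**What the plan says.** Section 4.4.1 introduces its list with "Pre-specified reasons for discontinuing include, but are not limited to, the following". Two entries turn on attendance:

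- Under Noncompliance, "a patient is to be withdrawn if he/she misses two consecutive visits".
- "Lost to Follow-up: Patient did not come in for a visit and could not be reached by phone".

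The consequences of withdrawal are the same for every reason. Section 4.4.1 says "No data will be collected for withdrawn subjects and withdrawn subjects may be replaced within the accrual period", and 4.4.2 says "no additional attempts will be made to contact the Participant".

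Section 6 and the Schedule of Events give three contacts after baseline. The first is headed "Visit 2 (Week 4 Phone Follow-up)" and has no LPPAI. Week 12 and Week 24 are clinic visits, each with an LPPAI. The primary endpoint in 3.4 is the percent reduction in LPPAI from baseline after 6 months, so it needs the baseline and Week 24 scores.

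On analysis, 7.3 says "Each participant who received the study drug will be included in the primary analysis regardless of study withdrawal for any reason". Section 7.2 leaves missing values missing, without imputation.

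**The concern.** A rule based on two consecutive missed visits suits a schedule with many visits. Here there are only three after baseline, and the last one carries the primary endpoint. The rule therefore either acts before that assessment and blocks it, or acts when the assessment has already been missed. The Lost to Follow-up reason can block it sooner, after a single missed Week 12 visit, and 4.4.1 does not say how many calls must fail or over what period.

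What is at stake is avoidable missing primary data. A participant withdrawn at Week 12 on attendance grounds still belongs to the primary analysis under 7.3, but has no Week 24 score and will not be asked for one.

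**Working it through.** The plan states no missed-visit or dropout rate, and 7.1 gives no sample size calculation, so there is no figure of the plan's own to reproduce. The check lists every attendance pattern and then sizes the effect under stated assumptions.

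**Step 1: when each rule can act.** With three contacts (Weeks 4, 12, 24) there are 2³ = 8 patterns. For the two-visit clause, the Week 4 call is counted as a visit, because Section 6 and the Schedule of Events number it as Visit 2. For Lost to Follow-up, the participant is taken to be unreachable by phone, and the Week 4 call is left out because it is not a visit one attends.

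| Contacts missed | Two-visit clause acts at | Lost to Follow-up acts at |
|---|---|---|
| none | – | – |
| 4 | – | – |
| 12 | – | Week 12 |
| 24 | – | Week 24 |
| 4, 12 | Week 12 | Week 12 |
| 4, 24 | – | Week 24 |
| 12, 24 | Week 24 | Week 12 |
| 4, 12, 24 | Week 12 | Week 12 |

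The two-visit clause acts in 3 of the 8 patterns. In only one of them (Weeks 4 and 12 missed, Week 24 not) would the participant have come to Week 24. Lost to Follow-up blocks an attendable Week 24 in two patterns: Week 12 alone missed, and Weeks 4 and 12 missed. If the Week 4 call does not count as a visit, the only consecutive pair is Weeks 12 and 24, and the two-visit clause never acts before the end.

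**Step 2: how many participants.** Assumptions, none of them from the plan: each contact is missed with probability p between 5% and 20%, independently, and half of those who miss Week 12 cannot be reached by phone.

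- Two-visit route: p² = 0.05² = 0.25% to 0.20² = 4%. Times 20, this is 0.05 to 0.8 participants.
- One-visit route: 0.5 × p = 2.5% to 10%. Times 20, this is 0.5 to 2 participants.

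The routes overlap, so the figures should not be added. Both count people withdrawn, not scores that could have been obtained. Multiplying by the chance 1 − p of attending Week 24, under the same independence, gives 0.05 × 0.95 = 0.0475 to 0.8 × 0.80 = 0.64 for the first route, and 0.5 × 0.95 = 0.475 to 2 × 0.80 = 1.6 for the second. In practice, people who miss visits and do not answer calls are less likely than others to return, so the recoverable number is probably lower still.

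**Step 3: what one lost score does.** One participant is 1/20 = 5 percentage points of the response rate. As an illustration, suppose 10 responders are observed and 2 scores are lost. The observed-case rate is 10/18 = 55.6%. Over all 20 it lies between 10/20 = 50% and 12/20 = 60%, depending on the two unseen outcomes.

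**The case against.** **Contradiction.** A reader might infer that the two bullets contradict each other, one withdrawing after a single miss and the other retaining the participant until a second. The text does not support this. Lost to Follow-up also requires that phone contact fails. The Noncompliance bullet sets a point at which withdrawal becomes mandatory; it does not promise retention until then, and its opening words already cover failure to keep to the visit schedule. The list is also open-ended. Both reasons can be applied together; what stands is overlap and vagueness.

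**Selection by the investigator.** A reader might also infer that open-label staff could choose whom to withdraw according to response. In these scenarios they have almost nothing to go on. Someone who misses Week 12 and cannot be reached has no post-baseline LPPAI or photographs; the only earlier contact is described as "Phone follow-up visit to assess any adverse reactions (if any)". Someone who misses Weeks 4 and 12 has had no scheduled contact since baseline.

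**A long unsupervised gap.** The interval from Week 4 to Week 24 is 20 × 7 = 140 days, and one might infer that no rule acts during it. That is true of the two-visit clause alone. Lost to Follow-up and the general Noncompliance wording can both act at Week 12.

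**Drug supply and oversight.** Section 5.5 dispenses one tube at baseline, two after the Week 4 call and three at Week 12, at one tube per 30 days. If a missed contact means no dispensing, a participant who misses Weeks 4 and 12 has had about 30 days' supply, and a Week 24 score would not reflect 6 months of treatment. Missed visits also mean missed pregnancy tests and skin checks. This stands as a reason to review study drug. It is not a reason to stop assessing someone whom 7.3 counts in the primary analysis whatever happened.

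**Scale.** This is a descriptive 20-patient pilot, and 7.3 plans a sensitivity analysis that excludes withdrawn participants. The modest scale is fair. But where the Week 24 score was never collected and is simply left missing, excluding that person changes nothing in the primary estimate, so the sensitivity analysis cannot show the effect of the loss.

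**A wider problem.** The bar on data after withdrawal applies to every reason, including adverse events and treatment failure. That is correct. The attendance rules are one route into it, and the fix should amend the general sentences as well.

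**Conclusion.** The point holds as a mismatch between the attendance rules, the visit schedule and the analysis population. The two-visit clause can act only at Week 12, where 4.4.1 and 4.4.2 then block the Week 24 LPPAI, or at Week 24, where it has no effect. Lost to Follow-up can block the same assessment after one missed Week 12 visit and an unspecified number of calls. Neither fits 7.3, which counts all treated participants, or 7.2, which does not impute.

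The enumeration rests only on the documents. The size rests on assumed rates and is probably small: under one participant of 20 by the two-visit route, and at most 0.5 to 2 by the one-visit route. The latter should not be read as recoverable scores, since some of those participants would not attend Week 24 anyway. With 20 participants, even one lost score is 5 percentage points, and the remedy is cheap, so the change is worth making.

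**What to change.** Amend 4.4.1 and 4.4.2, on assessment and contact only:

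- A missed Week 4 or Week 12 contact, or both, is recorded as missed and does not by itself end study assessment.
- Lost to follow-up is declared only when the Week 24 window closes without contact.
- The Week 24 LPPAI, PGA and DLQI are sought from every treated participant who has not refused.
- The sentences barring data collection and contact after withdrawal are amended to allow this, so that they agree with 7.3.

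Leave the dosing and regimen parts of the Noncompliance bullet as they are. Whether study drug continues after missed visits is a separate clinical decision, and no rule is proposed here.

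The cost is a few sentences and some extra phone calls by existing staff. The downside is that some Week 24 scores will come from participants with little drug exposure, which may lower the response rate slightly.
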